6.2.5.3 Assessing and Documenting Adverse Events

Adverse events will be assessed from the time the subject receives the first vaccination through Day 43 for Groups A-D and G-J and through Day 163 for Groups E, F, K, L. Medically attended adverse events, PIMMCs (Appendix 2, Section 12.2), and SAEs will be assessed from the time the subject receives the first vaccination until exit from the study. Additional details regarding eliciting and documenting local and systemic reactions are provided in Section 6.2.5.2.

At every study visit (except Visit 1), subjects will be asked a standard nonleading question to elicit any medically related changes in their well-being. They will also be asked if they have been hospitalized, had any accidents, used any new medications, received any vaccinations,

BARDA CSNH5 Influenza Vaccine With Either AS03 or MF59Protocol: BP-I-16-005 Version 2.026 February 2018or changed concomitant medication regimens (both prescription and over-the-counter
medications).medication

Subjects will be provided with diary cards to assist them in recording and reporting both unsolicited AEs and solicited local and systemic reactions (Section 6.2.5.2), according to Table 6–1.

Laboratory findings that qualify as AEs and nonqualifying laboratory abnormalities outside the laboratory's reference range will be toxicity graded according to the FDA Toxicity Grading Scale (Appendix 3, Section 12.3). Similarly, vital signs outside the clinic reference range will be graded according to the same scale. The toxicity grade for each identified laboratory finding and out-of-reference range vital sign will be documented in the study dataset.

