Any AE that meets SAE or PIMMC criteria (Section 6.2.5.1 and Appendix 2, Section 12.2) must be reported to PPD immediately (ie, within 24 hours) after the time site personnel first learn about the event. The following contact information is to be used for SAE reporting:

SAE Hotline:	
SAE Fax line:	

The safety event reporting periods are shown in Figure 6-1 for Groups A to D and G to J and Figure 6-2 for Groups E, F, K, and L. Solicited AEs will be collected for 7 days after each vaccination. Unsolicited AEs will be collected for 21 days after each of 2 vaccine doses (Groups A-D and G-J) and for 21 days after each of 3 vaccine doses (Groups E, F, K, and L). Serious adverse events and PIMMCs will be collected for approximately 13 months after the first study vaccine dose (Groups A-D and G-J) and for 2J and G-J) and for approximately 17 months after the first study vaccine dose (Groups E, F, K, and L).

[figure not shown]
H5 Influenza Vaccine With Either AS03 or MF59

26 February 2018

Protocol: BP-I-16-005 Version 2.0

[figure not shown]
Figure 6-1

Safety Event Reporting Period, Groups A to D, G to J

Abbreviations: AE, adverse event; MAAE, medically attended adverse event; PIMMC, potentially immune-mediated medical condition; SAE, serious adverse event; Sol, solicited; Unsol, unsolicited.

Figure 6-2 Safety Event Reporting Period, Groups E, F, K, L

Abbreviations: AE, adverse event; MAAE, medically attended adverse event; PIMMC, potentially immune-mediated medical condition; SAE, serious adverse event; Sol, solicited; Unsol, unsolicited.

Protocol: BP-I-16-005 Version 2.0

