Examine vaccination site ^r		Xs		Х	X ^s		X ^d		Xs		Х					Xď	Xt
AE/MAAE/PIMMC/ SAE assessment ^u		Х	Х	Х	X	Х	Х	Х	Х	Х	Х	Х	Х	Х	Х	Х	X

Table 12–2Schedule of Events, Groups E, F, K, L

Abbreviations: AE, adverse event; ALT, alanine aminotransferase; AST, aspartate aminotransferase; DC, diary card; eCRF, electronic case report form; EOS, end of study; ET, early termination; FDA, Food and Drug Administration; MAAE, medically attended adverse event; N/A, not applicable; PIMMC, potentially immune-mediated medical condition; SAE, serious adverse event; SUSAR, suspected unexpected serious adverse reaction; ULN, upper limit of normal; Unsch, unscheduled; V, visit; WOCBP, women of childbearing potential.

- ^a Telephone call assessment.
- ^b Prior to the completion of any study-related procedures.
- Vital sign measurements include oral temperature, pulse rate, and blood pressure. Vital signs will be measured before blood is collected, at both pre-vaccination and 30±5-minute postvaccination time points on a vaccination day. Diastolic and systolic blood pressure will be measured after the subject is seated for at least 5 minutes.
- ^d If clinically indicated.
- e Prior to vaccination.
- ^f Ask subject a standard nonleading question to elicit any medically related changes in their well-being. Ask if they have been hospitalized, had any accidents, used any new medications, received any vaccinations, or changed concomitant medication regimens (both prescription and over-the-counter medications).

Protocol: BP-I-16-005 Version 2.0

- 26 February 2018
- ^g Diary Card I (Days 1-8), III (Days 22-29), and V (Days 142-149) will be used to collect unsolicited and solicited local and systemic reactions. Diary Card II (Days 9-21), IV (Days 30-43), VI (Days 150-163) will be used to collect unsolicited AEs.
- ^h If applicable, according to the protocol period, collect and review DC with subject.
- ⁱ Use of all concomitant medications that the subject is taking at the time of Visit 1, medications taken up to 14 days prior to Visit 1, and vaccines received 12 months prior to Visit 1 will be recorded in the subject's eCRF.
- ^j Obtained by interview and by review of diary card completed by the subject.
- ^k Any physical examination findings will be collected in the eCRF for medical history data presentation.

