- ¹ Targeted physical examination will be performed at the discretion of the investigator, if necessary, to evaluate AEs or clinical laboratory abnormalities. Any findings from this examination will be collected in the eCRF for AEs.
- ^m A urine pregnancy test must be performed within 24 hours prior to vaccination and pregnancy test results must be final and negative prior to vaccination.
- ⁿ Hematology: complete blood count with differential, platelet count; coagulation: partial thromboplastin time and prothrombin time (international normalized ratio); chemistry/metabolic panel: ALT, AST, total bilirubin, creatinine, and blood urea nitrogen.
- ^o For abnormal laboratory results that are clinically significant and for ALT and/or AST elevations ≥2.6 × ULN, repeat test until resolved or results become stable (see Section 6.2.5.8).
- ^p Subjects with an acute illness, including body temperature greater than 100.4°F, immediately prior to each vaccination or, per subject report, within 3 days prior to a scheduled vaccination in this study can be rescheduled for vaccination as long as the vaccination visit is within the visit window. Subjects with a Grade ≥3 AE that has not returned to baseline or stabilized will not be revaccinated. Subjects with a serum ALT and/or AST elevation that is Grade 2 (moderate) or greater based on FDA toxicity grading (ie, ≥2.6 × ULN) will not be revaccinated unless the value resolves on repeat testing to the screening baseline value (ie, baseline toxicity score) and the subject remains within the visit window allowance (see Section 4.3).
- ^q At Visits 1, 4, and 8, subjects will be monitored for solicited and unsolicited AEs, SAEs, MAAEs, PIMMCs, and SUSARs for at least 30 minutes after vaccination; concomitant medications will be recorded.
- r Examine vaccination site for erythema/redness and swelling and monitor for pain.
- ^s At Visits 1, 4, and 8, complete a 30±5-minute postvaccination injection site examination for erythema/redness and swelling and monitor for pain. If a visible injection-site abnormality is observed, document with a photograph.
- t If the unscheduled visit occurs within 7 days after any of the study vaccinations.
- ^u Only MAAEs, PIMMCs (see Appendix 2, Section 12.2), and SAEs will be collected after Day 163; all other AEs will be collected through 21 days following each vaccination.

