All AEs reported after the first dose of IP will be summarized in tables. AEs within 21 days of each dose of IP, and before the date and time of the next dose of IP (if applicable) will be summarized in tables based on each dose only (Dose 1, 2 for Groups A-D, G-J; Dose 1, 2, 3 for Group E, F, K and L). When the time of an AE is missing and the AE start date is on the date of vaccination, then that AE will be considered as happening after the corresponding dose of IP.

All AEs will be summarized by presenting the number and percentage of subjects having any AEs and having each individual adverse event based on SOC and PT, and PT only. At each level of subject summarization, a subject is counted once if the subject reported one or more events. Percentages will be calculated out of the number of subjects as treated per study group in the Safety Set. For the dose-specific AE summaries, percentages will be calculated out of the number of subjects as treated per study group corresponding to Dose 1, Dose 2 or Dose 3.

Unless otherwise stated, AEs will be sorted in descending order by frequency of SOC and PT.

The following summaries, based on Dose 1 only, Dose 2 only, and both Dose 1 and Dose 2 for Groups A-D, G-J and Dose 1 only, Dose 2 only, Dose 3 only, and all Dose 1, Dose 2 and Dose 3 for Groups E, F, K and L will be provided:

- Overview summary of the number and percentage of subjects with any AE, SAE, AE related to IP, AE leading to study withdrawal, AE leading to death, solicited local AE, severe solicited local AE, solicited systemic AE, severe solicited systemic AE, MAAE, PIMMC, unsolicited AE, severe unsolicited AE, and unsolicited AE related to IP
- All AEs by SOC and PT
- All AEs by AE Type and PT
- All AEs by SOC, PT and Severity

- All AEs by SOC, PT and Relationship
- All unsolicited AEs by SOC, PT and Day of Onset

The following summaries with 95% exact CIs using Clopper Pearson method, based on events recorded during the 8 days post each vaccination will be provided as the analysis of primary safety endpoint:

- Solicited Local AEs by Severity
- Solicited Systemic AEs by Severity

All MAAEs and PIMMCs after the first dose of IP will be summarized in a table by SOC, PT and Severity.

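### Protocol 6.2.5.3 runs AE collection unbroken to Day 163 in the 3-dose groups and SAP 9.1 sets no onset window for the all-doses AE tables, so ordinary events from Days 44 to 141 may enter those percentages

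*Protocol*

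**What the plan says.** **Continuous reading.** The opening of Protocol 6.2.5.3 runs AE assessment from the first vaccination "through Day 43 for Groups A-D and G-J and through Day 163 for Groups E, F, K, L".

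**Windowed reading.** Protocol 6.2.5.4 collects unsolicited events in the 3-dose groups "for 21 days after each of 3 vaccine doses (Groups E, F, K, and L". Table 6-1, which 6.2.5.3 itself cites, assigns unsolicited events to the diary-card periods. Footnote g of Table 12-2 gives the same periods: "Diary Card I (Days 1-8), III (Days 22-29), and V (Days 142-149) will be used to collect unsolicited and solicited local and systemic reactions", and "Diary Card II (Days 9-21), IV (Days 30-43), VI (Days 150-163) will be used to collect unsolicited AEs". The secondary endpoint (Protocol 7.2, SAP 3.2.2.1), the analysis text in Protocol 7.7.4.1 and SAP Table 4-1 all use 21 days after each vaccination.

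**Footnote u.** In Table 12-1 (2-dose groups), collection narrows to MAAEs, PIMMCs and SAEs after Day 43. In Table 12-2 (3-dose groups) the narrowing comes later: only MAAEs, PIMMCs and "SAEs will be collected after Day 163; all other AEs will be collected through 21 days following each vaccination". The first clause can be read as allowing ordinary events up to Day 163. The second clause does not allow that.

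**Analysis.** SAP 9.1 states: "All AEs reported after the first dose of IP will be summarized in tables". The sentence that follows applies a 21-day limit, but only to the tables for a single dose. The same summaries are also produced for all doses together.

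**The concern.** For Groups E, F, K and L the protocol gives two answers to whether an ordinary unsolicited event between the Dose 2 window and Dose 3 should be recorded. The SAP does not settle the question at analysis, because the all-doses tables take every AE after Dose 1 whatever its onset day.

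At stake are the descriptive percentages in those tables: the overview, SOC/PT, severity, relationship and day-of-onset summaries, where the later onset category (more than 8 days after a dose) has no upper end. SAP 3.3 prints the six groups of one adjuvant on a page. The 2-dose groups would therefore stand beside 3-dose groups that may have been observed under a different rule. The all-doses unsolicited tables would also no longer match the secondary endpoint, which is defined by 21-day windows.

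**Working it through.** **1. The plan's own days.** Dose 2 window: 22 + 21 = Day 43. Dose 3: 22 + 120 = Day 142. Dose 3 window: 142 + 21 = Day 163. All agree with the protocol.

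**2. Days covered under each rule** (nominal days, diary-card periods from Table 6-1 and footnote g).

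| Groups | Continuous rule (6.2.5.3) | Post-dose windows (Table 6-1) | Difference |
|---|---|---|---|
| 2-dose (A-D, G-J) | Days 1-43 = 43 | Days 1-43 = 43 | 0 |
| 3-dose (E, F, K, L) | Days 1-163 = 163 | Days 1-43 and 142-163 = 43 + 22 = 65 | 163 − 65 = 98 (Days 44-141) |

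The conflict exists only in the 3-dose groups. Against the 2-dose groups the continuous rule gives 163 − 43 = 120 more days, of which 22 are the intended Dose 3 window and 98 are the excess.

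**3. Sensitivity of the 98 days.** If SAP Table 4-1 is read strictly, with the vaccination day as Day 1, the windows cover 3 × 21 = 63 days and the excess is 163 − 63 = 100. With the protocol's visit windows (Visit 4 +3, Visit 7 ±3, Visit 8 ±7), the gap for one subject is the Visit 8 day − 1 − the Visit 7 day:
- shortest: 135 − 1 − (25 + 21 + 3) = 85 days
- longest: 149 − 1 − (22 + 21 − 3) = 108 days

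**4. Can gap events reach the database?** Table 12-2 schedules no visit, call or diary card between Visit 7 (Day 43) and Visit 8 (Day 142). Visit 8 does have a subject interview and an AE assessment, and Protocol 6.2.5.4 sends every AE that is reported or observed to the AE page of the eCRF. Entry is therefore possible, but it would depend on recall and on how the site reads the text.

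**5. Possible size.** The documents give no unsolicited AE rate. Assume a constant rate r per person-year and full capture, so that P(at least one event) = 1 − exp(−r × days / 365.25).

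| Assumed r | 65 days | 163 days |
|---|---|---|
| 0.5 | 8.5% | 20.0% |
| 1 | 16.3% | 36.0% |
| 2 | 29.9% | 59.0% |

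In a group of 60 at r = 1, that is about 9.8 subjects against 21.6.

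For each assumed rate the right-hand column is an upper bound. Capture without a diary would be incomplete, and some gap events would be SAEs, MAAEs or PIMMCs, which are properly collected in every group. The rows for unsolicited events are the most exposed. In the any-AE row, a subject already counted for a solicited reaction cannot be counted again.

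**The case against.** The strongest reply is that the sentence in 6.2.5.3 is only an outer limit. The same section says that Table 6-1 supplies the reporting periods, and the 21-day rule recurs in the objectives, endpoints, 6.2.5.4, 7.7.4.1 and SAP Table 4-1. One summary sentence stands against many specific ones. This makes the windowed reading the likelier intention. It does not remove the conflict, because footnote u of Table 12-2 repeats the ambiguity. Nor does it help at analysis: SAP Table 4-1 describes collection, while SAP 9.1 is the text that selects events for tables.

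Several further points on that side stand:
- There is no scheduled contact in the gap until Day 142, so few events may enter.
- The dose-specific tables carry the 21-day limit and report the secondary endpoint as defined.
- No between-group safety test is planned. The exploratory comparisons in SAP 8.3 are of immunogenicity only.
- All-doses tables cover two doses in some groups and three in others, so they were never exactly like for like. Groups E and F against K and L share one schedule.

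A reader might also infer that sites reading the text differently make the groups or sites non-comparable. The documents do not support that as a separate problem. Randomization is stratified by site, so any mix of readings is spread about evenly over the groups, and SAP 9.1 plans no AE table by site.

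**Conclusion.** The point holds in a limited form. The collection passages conflict for Groups E, F, K and L over 98 nominal days (85 to 108 for a single subject), and SAP 9.1 leaves the all-doses tables without an onset window. Ordinary events from Days 44 to 141 may therefore be counted in those tables.

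The exposure is confined to descriptive all-doses AE summaries. The dose-specific tables, the 8-day solicited primary endpoint and the SAE, MAAE and PIMMC summaries are unaffected.

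The size is unknown from the documents. Under the assumed rates of 0.5 to 2 per person-year and full capture, the proportion with at least one event about doubles, and for those rates that is a ceiling.

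Two stronger readings are tempting. One is that gap events will be counted. The documents show only that they can be, since no diary or scheduled contact covers the gap. The other is that the secondary endpoint is compromised. It is not, because the tables that report it per dose carry the 21-day limit.

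**What to change.** 1. **Protocol.** Reword the opening sentence of 6.2.5.3 and footnote u of Table 12-2 so that both agree with Table 6-1 on ordinary unsolicited events between the Dose 2 and Dose 3 windows.
2. **SAP 9.1.** Restrict the all-doses unsolicited AE tables to onset within the same post-dose window as the dose-specific tables. This makes them match the secondary endpoint even if some sites recorded gap events.
3. **SAP 9.1.** Tabulate SAEs, MAAEs and PIMMCs separately over the full period, so that the filter drops none of them. MAAEs and PIMMCs already have a table. SAEs have an overview row and a listing, so a short SAE table by SOC and PT is needed; Protocol 7.7.4.1 already calls for that summary.

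The cost is one protocol sentence, one footnote, one programming filter and one small table. No new data are needed. The 3-dose groups will still have the intended Dose 3 window (22 nominal days) beyond the 2-dose groups, and a table footnote should say so.

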3.1.3 Study Pausing Rules

Study pausing rules will be monitored throughout the study by the medical monitor. The sponsor will pause study enrollment and study vaccine administration and the IDMC will review unblinded safety data if any of the following are met:

- Occurrence of one or more SAE(s), MAAE(s), or PIMMC(s) judged to be related to IP; OR
- Any potentially life-threatening AE judged to be related to IP (An AE or suspected adverse reaction is considered "life threatening" if, in the view of either the investigator or sponsor, its occurrence places the patient or subject at immediate risk of death. It does not include an AE or suspected adverse reaction that, had it occurred in a more severe form, might have caused death); OR
- A death, if judged to be related to IP; OR
- Anaphylaxis or bronchospasm within 4 hours of injection judged to be related to IP; OR
- 10% of vaccinated subjects at a given vaccination time point when at least 50% of subjects in that group have been vaccinated experience the same or similar systemic or local Grade 3 (toxicity scoring) or higher event; OR
- A pattern of significant symptoms, physical findings, or laboratory abnormalities that, although individually minor, collectively represent a safety concern in the opinion of the investigator or the medical monitor.

H5 Influenza Vaccine With Either AS03 or MF59

26 February 2018

Protocol: BP-I-16-005 Version 2.0

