6.2.5 Adverse Events

6.2.5.1 Definitions of Adverse Events

The investigator is responsible for reporting all treatment-emergent AEs that are observed or reported during the study, regardless of their relationship to IP or their clinical significance.

An AE is defined as any untoward medical occurrence in a subject enrolled into this study regardless of its causal relationship to IP. Subjects will be instructed to contact the investigator at any time after randomization if any symptoms develop.

An SAE is defined as any event that results in any of the following:

- Death,
- Is immediately life threatening,
- Requires inpatient hospitalization or prolongation of existing hospitalization,
- Results in persistent or significant disability/incapacity, or
- Is a congenital anomaly/birth defect.

Important medical events that may not result in death, be life threatening, or require hospitalization may be considered SAEs when, based upon appropriate medical judgment, they may jeopardize the subject or may require medical or surgical intervention to prevent one of the outcomes listed in this definition. Examples of such medical events include allergic bronchospasm requiring intensive treatment in an emergency room or at home, a blood dyscrasia or convulsion that does not result in inpatient hospitalization, or the development of drug dependency or drug abuse.

Medically attended AEs are defined as AEs with medically attended visits, including hospital, emergency room, urgent care clinic, or other visits to or from medical personnel (medical doctor, physician assistant, nurse practitioner) for any reason.

BARDA CSNH5 Influenza Vaccine With Either AS03 or MF59Protocol: BP-I-16-005 Version 2.026 February 2018Potentially immune-mediated medical conditions are considered adverse events of specialinterest. The PIMMCs of concern for this study are detailed in Appendix 2, Section 12.2.

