6.2.5.7 Assessing Expectedness

Expected AEs are AEs consistent with the applicable product information provided by the sponsor (the investigator brochures for IP). The sponsor, in consultation with the medical monitor, determines expectedness of SAEs and MAAEs. The sponsor and medical monitor should consider the package inserts of all products administered in this study when determining expectedness. If the assessment is that the SAE or MAAE is expected, no further reporting is required. If the medical monitor's assessment is that the SAE or MAAE is unexpected, then the event may represent a SUSAR or expedited SAE for reporting purposes.

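### One related MAAE pauses the whole study, but a related MAAE that is neither an SAE nor a PIMMC has no stated notification time

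*Protocol*

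**What the plan says.** **The trigger.** Protocol Section 3.1.3 states "The sponsor will pause study enrollment and study vaccine administration" and sends unblinded safety data to the IDMC if any of six conditions is met. The first is "Occurrence of one or more SAE(s), MAAE(s), or PIMMC(s) judged to be related to IP". The fourth is "Anaphylaxis or bronchospasm within 4 hours of injection judged to be related to IP". SAP 11.1 repeats the list. On who watches it, Section 3.1.3 says: "Study pausing rules will be monitored throughout the study by the medical monitor".

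**The clock.** Section 6.2.5.4 covers "Any AE that meets SAE or PIMMC criteria (Section 6.2.5.1 and Appendix 2, Section 12.2"; such an event "must be reported to PPD immediately (ie, within 24 hours) after the time site personnel first learn about the event". MAAEs are not named there. In Section 9.6 the investigator's commitment to the protocol's timeline names SAEs only.

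**The definition.** Section 6.2.5.1 counts an AE as medically attended after a hospital, emergency room or urgent care visit, or "other visits to or from medical personnel (medical doctor, physician assistant, nurse practitioner) for any reason".

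**The route for everything else.** Under Section 6.2.5.4 all AEs go on the eCRF AE page with severity, relationship and seriousness. No entry deadline is given. A footnote to Table 6–1 obliges the investigator to report a related MAAE learned of after study exit, also without a time limit. Section 10.1.4 has the medical monitor review study records and source documents, watch for the pausing rules, and review causality for SAEs, MAAEs and PIMMCs. It states no interval.

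**The concern.** A pausing rule that one event can trigger works only as fast as that event reaches the person applying the rule. Here the rule depends on three event classes and the reporting clock covers two of them. A site could follow Section 6.2.5.4 exactly and still leave a related MAAE in the eCRF for an unspecified time after the protocol's own condition for pausing had been met.

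The stake is the timing of the pause and of independent review. Sections 3.1 and 10.1.5 say the IDMC meets only if a pausing rule is met, so late recognition of the trigger also delays the committee.

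**Working it through.** **1. Set the six pausing conditions against the 24-hour list.**

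- Related SAE or PIMMC: on the list.
- Related MAAE that is also an SAE or PIMMC: on the list.
- Related MAAE that is neither: not on the list.
- Related life-threatening AE, and related death: both meet SAE criteria, so on the list.
- Related anaphylaxis or bronchospasm within 4 hours: on the list if SAE criteria are met. Section 6.2.5.1 gives allergic bronchospasm needing intensive treatment as an example of an event that may be an SAE. A milder related bronchospasm is a small remainder without a clock.
- The 10% rule for Grade 3 or higher events, and the pattern rule: these rest on pooled data or on judgement, not on one report.

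The gap is thus one part of the first condition, plus a small part of the fourth.

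**2. Ask whether the SAE class covers the missing part.** It does not. An office visit to a nurse practitioner for a vaccine reaction satisfies the MAAE definition and none of the SAE criteria. SAP 9.1 goes further and treats all solicited reactions as related, though Protocol Section 6.2.5.2 leaves that to the investigator. Under the SAP wording, any such visit for arm pain or fever would be a related MAAE.

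**3. Ask whether another section supplies a clock.** Sections 6.2.5.4 (eCRF entry), 9.6 and 10.1.4, and the Table 6–1 footnote, were compared. None gives a time for this class.

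**4. Reproduce the plan's nearest figure.** Table 7–1 gives the chance of seeing at least one SAE, MAAE or Grade 3 solicited AE. The formula is 1 − (1 − p)^n.

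- p = 1%, n = 60: 1 − 0.99^60 = 45.3% (table: 45.3).
- p = 1%, n = 120: 1 − 0.99^120 = 70.1% (table: 70.1).

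All 14 cells agree to within 0.1 percentage point.

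**5. Apply the same formula study-wide.** The pause applies to all groups, so n = 720. The documents give no rate of related MAAEs; the rates below are assumptions, with subjects taken as independent.

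| Assumed related-MAAE rate per subject | Chance of at least one in 720 |
|---|---|
| 0.01% | 6.9% |
| 0.05% | 30.2% |
| 0.1% | 51.3% |
| 0.2% | 76.3% |
| 0.5% | 97.3% |
| 1% | 99.9% (720 × 0.01 = 7.2 subjects expected) |

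An even chance needs about 0.10%; a 95% chance needs about 0.42%. These rates count any related MAAE. The class without a clock is the part that is neither SAE nor PIMMC.

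**6. Exposure.** Planned doses are 8 × 60 × 2 + 4 × 60 × 3 = 960 + 720 = 1,680. How many would fall within a delay cannot be computed, because neither the enrolment rate nor an eCRF entry time is stated.

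**The case against.** The best defence is that the medical monitor is not cut off. Section 10.1.4 gives that person continuing access to records and an explicit role in MAAE causality, and the eCRF captures relatedness. Section 10.1.2 lets the principal investigator suspend the study or delay a dose. Entry and notification times may also sit in documents not supplied, such as the IDMC charter, the eCRF instructions or the AE reporting procedure mentioned in Section 7.8. This stands as far as it goes: a route exists, so the defect is an unstated time and not a missing channel. It does not supply the time, and Section 9.6 ties investigators to the timeline in the protocol itself.

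Several stronger readings are tempting but not supported:

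- A reader might infer that vaccination would necessarily continue after the trigger. The documents show only that the delay has no stated limit.
- A reader might take Section 6.2.5.7, "If the assessment is that the SAE or MAAE is expected, no further reporting is required", as exempting expected MAAEs from the pausing check. That sentence follows an assessment made by the sponsor with the medical monitor, and the next one concerns SUSAR and expedited reporting. It reads as onward regulatory reporting of an event the monitor already holds.
- A reader might blame the monitor's blinding. The trigger depends on relatedness to the product, not on group.
- A reader might call the pausing rules the only way to the IDMC. Sections 3.1 and 10.1.5 say so, but Section 5.5 describes ad hoc review for any immediate concern, so the text is not uniform.

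**Conclusion.** The point holds in a limited form. A stated pausing rule depends on an event class that the stated 24-hour rule leaves out, and the sections compared give no time for it. The gap covers related MAAEs that are neither SAEs nor PIMMCs, and a small remainder of related bronchospasm within 4 hours that does not meet SAE criteria.

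The consequence is a possible delay, of undefined length, to the pause and to the IDMC review it triggers. The trigger need not be rare: under the assumed rates, the chance of at least one related MAAE study-wide runs from 6.9% at 0.01% per subject to 99.9% at 1%. No dose count can be attached to the delay. The practical gap would be smaller if an operational document not supplied sets a time, but the protocol text would still need aligning. This should be corrected; it does not affect the immunogenicity or reactogenicity analyses.

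**What to change.** Reconcile Protocol Sections 3.1.3, 6.2.5.4, 9.6 and 10.1.4 and SAP 11.1 so that every event class that triggers a pause has a stated notification time to the medical monitor. Whether the pausing rule or the reporting list changes is for the sponsor to decide.

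If the pausing rule stays as written, add to the 24-hour list in Section 6.2.5.4 any MAAE judged related to the product, and any related bronchospasm within 4 hours that does not already meet SAE criteria. Extend the commitment in Section 9.6 to match.

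As an optional clarification only, state in Section 6.2.5.7 that the waiver of further reporting refers to regulatory reporting.

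The cost is a short amendment, an update to the site safety form, and some additional 24-hour reports of mild related MAAEs. No visit or procedure is added.
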